### ii. SECONDARY OBJECTIVES

The secondary objectives of this study are to:

- Study survival rates by components and etiology (revision and revision with reconstruction)
- Studying patient satisfaction with their hip prosthesis
- Confirm the safety of these implants by studying any complications observed
- Evaluate performance through the clinical scores of HARRIS (HHS) and forgotten prosthesis score (SHO-12) of femoral stems SAGITTA® EVL R.

The criteria for each of the objectives are presented in Chapter 6.A.iii.

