#### **Functional Clinical Scores and Ratings**

- *Harris Hip Score*:

The Harris score (HHS) is one of the main functional clinical scores used after hip replacement surgery and evaluates 3 "items" relating to the diseased or operated hip:

- Pain (44 points)
- Function (47 points)
- Mobility (9 points)

For a maximum total score of 100 (minimum score:0), the HHS results will be categorized as follows:

 Harris WH. Traumatic arthritis of the hip after dislocation and acetabular fractures: treatment by mold arthroplasty. An end-result study using a new method of result evaluation. *J Bone Joint Surg Am.* 1969; 51: 737–55.

HHS	
Excellent	90-100
Good	80-89
Correct	70-79
Bad	< 70

The HHS fill grid is available in **Appendix 5**.

- *Forgotten Hip Score (FJS-12):*

The Forgotten Hip Score (SHO-12) is the French version of the FJS-12 (*Forgotten Joint Score*). The objective of this self-questionnaire is to estimate the degree of neglect of the hip and knee prosthesis through 12 questions.

Each item has 5 levels of response:      Never: 0 points

Almost never: 1 point  
Rarely: 2 points  
Sometimes: 3 points  
Often: 4 points

The sum of the items is divided by the number of items and multiplied by 25 to obtain a score out of 100.

The OHSS Fill Grid is available in **Appendix 6**.

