**iv. METHODS AND TIMING OF EVALUATION, RECORDING AND ANALYSIS OF VARIABLES**

The table below presents the different stages and moments of patient follow-up, and the acquisition of related data.

Study Outline	Retrospective			Prospective part	
	Pre-operative data	Implantation	Immediate post-operative follow-up	Inclusion in the study	Medium-term monitoring
Topic Information				X	
Verification of inclusion criteria				X	
Demographics: Age, height, weight, sex	X				
Medical and surgical history	X				
Implantation of the prosthesis Operative report: Date of operation, type of anesthesia, approach, type of implant and assembly performed, coding of the surgical act (CCAM code)		X			
Radiological examination	X				X
Functional score assessment Modified HHS – SHO-12	X (except SHO-12)				X
Satisfaction					X
Adverse event collection		X	X	X	X

Complications and serious adverse events will be collected independently of the retrospective and prospective parts but over the entire period since the intervention.

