**APPENDIX 6: FORGOTTEN HIP SCORE – SHO12**

Are you aware of your hip...	1pt	2pts	3pts	4pts	5pts
	Never	Hardly ever	Rarely	Sometimes	Often
1. ... in your bed at night?					
2. ... When you sit in a chair for more than an hour?					
3. ... When you walk for more than 15 minutes?					
4. ... when you take a bath or shower?					
5. ... When you travel by car?					
6. ... When you climb the steps of a staircase?					
7. ... When you walk on uneven ground?					
8. ... When you get up from a low sitting position?					
9. ... When you stand for a long time?					
10.... When you do housework or gardening?					
11.... When you are walking or hiking?					
12.... when you practice your favorite sport?					
12b... during your sexual intercourse?					

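### The SHO-12 scoring rule in section 6.A.iii gives an inverted scale (a hip never noticed scores 0), and the Appendix 6 form prints item points that do not fit the rule

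*Protocol*

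**What the plan says.** SHO-12 is one of two scores that carry the performance objective. Section 5.C.ii reads: "Evaluate performance through the clinical scores of HARRIS (HHS) and forgotten prosthesis score (SHO-12) of femoral stems SAGITTA® EVL R".

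Section 6.A.iii gives the purpose of the instrument: "The objective of this self-questionnaire is to estimate the degree of neglect of the hip and knee prosthesis through 12 questions". In context, neglect can only mean how far the joint is forgotten. The same section codes five response levels, starting at "Never: 0 points" and ending at "Often: 4 points". It then sets the total: "The sum of the items is divided by the number of items and multiplied by 25 to obtain a score out of 100".

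The form in Appendix 6 opens its items with "Are you aware of your hip", followed by a list of situations. It heads the same five responses with 1 to 5 points and has a row 12b after row 12.

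For the companion score, section 6.A.iii says: "For a maximum total score of 100 (minimum score:0), the HHS results will be categorized as follows". Its top band, 90 to 100, is labelled excellent, and below 70 is bad.

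The schedule in section 6.A.iv marks the preoperative functional scores as "X (except SHO-12"), so SHO-12 is recorded only at the medium-term visit.

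**The concern.** The items count awareness, and the formula adds them up without turning them round. The result is a measure of awareness under the name of a measure of forgetting. No part of the protocol states a reversal or says that a low SHO-12 is the good result.

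An analyst who follows the rule would report a low value for patients who do well and a high value for those who do badly. It would stand next to an HHS on the same 0 to 100 range that runs the other way, with nothing to warn the reader. Because there is no preoperative SHO-12, no before-and-after comparison would expose the inversion.

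The form adds a second problem. Points read directly from Appendix 6 are one unit higher per item than the rule expects, so the total leaves the stated range.

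**Working it through.** **Inputs.** Item codes 0 to 4 and the formula come from section 6.A.iii. The item wording, the 1 to 5 points and row 12b come from Appendix 6.

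**The stated rule.** Score = (sum of items / number of items) × 25. With all 12 items at one level:

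| Response to all items | Section 6.A.iii codes (0–4) | Appendix 6 points (1–5) | 100 − score, codes 0–4 | 100 − score, points 1–5 |
|---|---|---|---|---|
| Never | 0/12 × 25 = 0 | 12/12 × 25 = 25 | 100 | 75 |
| Almost never | 12/12 × 25 = 25 | 24/12 × 25 = 50 | 75 | 50 |
| Rarely | 24/12 × 25 = 50 | 36/12 × 25 = 75 | 50 | 25 |
| Sometimes | 36/12 × 25 = 75 | 48/12 × 25 = 100 | 25 | 0 |
| Often | 48/12 × 25 = 100 | 60/12 × 25 = 125 | 0 | −25 |

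The 0 to 100 range that the protocol states is reproduced with codes 0 to 4, but it rises with awareness. With the form's points the direction is the same and the range is 25 to 125.

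**Two mixed patients, codes 0 to 4.**
- Nine Never and three Almost never, a nearly forgotten hip: 3/12 × 25 = 6.25. Reversed, 93.75.
- Nine Often and three Sometimes, a hip mostly noticed: (36 + 9)/12 × 25 = 93.75. Reversed, 6.25.

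**Size of the discrepancy.** The reversed score minus the reported score is (100 − S) − S = 100 − 2S. The protocol gives no expected SHO-12 value, so the following means are assumptions that only show the range:
- Mean item response 1.2: reported 1.2 × 25 = 30, reversed 70.
- Mean item response 2.8: reported 2.8 × 25 = 70, reversed 30.
- Mean item response 2.0: 50 either way. This coincidence applies to the cohort mean only. Individual scores are still inverted, and the minimum and maximum called for in section 7.B become 100 minus each other.

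**Form points under the rule.** Coding 1 to 5 adds exactly 25 to every score, because (mean + 1) × 25 = mean × 25 + 25. The nearly forgotten hip above would score (9 × 1 + 3 × 2)/12 × 25 = 31.25, which looks plausible. Only a patient with a high total would go past 100 and give the error away.

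**Number of items.** Appendix 6 has 13 rows if 12b is counted, against 12 questions in section 6.A.iii. If all 13 are summed and averaged over 13, the ends stay at 0 and 100. If 13 are summed and divided by 12, all Often gives 52/12 × 25 = 108.3. The protocol does not say which rows count.

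**The case against.** The strongest reply is that the direction is inferred. The protocol never says in words that a higher SHO-12 is better, and it gives no categories or target for it. Two scales may legitimately run in opposite directions, so disagreement with the HHS is not in itself an error. This much stands. But a score whose stated purpose is to estimate the degree of forgetting must rise as the hip is forgotten, and this one falls. At the least, the direction is unstated and conflicts with the name and purpose, so text is needed either way. The argument rests on the protocol's own wording and not on the cited instrument paper, which is not at hand.

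The second reply is that the harm is limited and reversible, and this also stands. Subtracting from 100 is exact: it leaves the standard deviation and the width of the confidence interval unchanged, and the item responses stay on the case report form. There is no hypothesis, test or pass/fail criterion (sections 5.D, 7.D and 7.G).

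A reader might infer that an improvement would be reported with the wrong sign, as a deterioration. The documents do not support that. Section 7.B calculates changes for SHO-12 only if available, and the schedule has no preoperative SHO-12. What is inverted is a single follow-up level, not a signed change. Nor does 100 mean a hip that is always noticed: the top response is Often.

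**Conclusion.** The concern holds as an inverted scale combined with a form whose points do not match the rule. Under section 6.A.iii a hip never noticed scores 0 and one often noticed scores 100; points taken from Appendix 6 give 25 to 125. The discrepancy for any patient or mean is 100 − 2S, where S is the score under the stated rule with codes 0 to 4.

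This rests on two readings: that neglect means forgetting, and that the intended score rises with it. Both follow from the score's name, its stated purpose and its use as a performance measure. The protocol itself does not state the reversed formula.

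This is a rule that the protocol fixes badly, not a detail left to an analysis plan. It should be corrected, but it does not threaten the study: it touches one descriptive secondary outcome, and the Kaplan-Meier stem survival is unaffected.

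**What to change.** - In section 6.A.iii, define SHO-12 = 100 − (mean of items coded 0 to 4 × 25), and state that a higher score means the hip is more forgotten, which is the better result, as for the HHS.
- In Appendix 6, change the printed points from 1–5 to 0–4. Reversal alone is not enough: with the form's present points it would give 75 down to −25.
- Reconcile rows 12 and 12b with the 12 questions, and say which rows enter the sum and the number of items.
- If any forms have already been completed, score from the ticked response and not from the printed points.

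The cost is a few lines of protocol wording and a corrected form. No new data or visits are needed, and any scores already calculated can be recomputed exactly from the item responses.

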**Radiographic evaluation:**

- *Paprosky's classification :*

This classification makes it possible to define the preoperative bone defect.

	Definition	Proximal Metaphysis	Diaphysis
I	Minimal proximal metaphyseal bone loss	Intact	Intact
II	Moderate-to-severe proximal metaphyseal bone loss	Absent	Intact
III	A Severe proximal metaphyseal bone loss with diaphysis intact for some distance	Absent	≥4 cm of isthmus
	B Severe proximal metaphyseal bone loss with diaphysis intact for some distance	Absent	< 4 cm of isthmus
IV	Complete loss of metaphyseal and diaphyseal bone	Absent	Absent

- *Preoperative fractures will be evaluated by the Vancouver Stadium^4:*

This classification of periprosthetic hip fractures proposed by Duncan and Masri is the most widely used classification system. It takes into account the site of the fracture, the condition of the femoral implant and the quality of the surrounding femoral bone material.

- **type A:** fractures involve the trochanteric area
  - **A(G):** greater trochanter
  - **A(L):** lesser trochanter
- **type B:** around the stem or just below it
  - **B1:** stem stable
  - **B2:** stem loose
  - **B3:** stem loose, bone stock inadequate
- **type C:** well below the stem

- *Osseointegration of the stem will be assessed by the Engh score (see Appendix 7)*

Measured on postoperative X-rays, it is divided into 2 subparts: fixation and stability.

The final score can be classified into 4 categories:

- $<-10^\circ$ : unstable
- $-10$  to  $<0^\circ$ : suboptimal but unstable
- $0$  to  $+10^\circ$ : suspected bone growth
- $>+10^\circ$ : osseointegration

[figure not shown]
- *Bone reconstruction will be measured by the cortico-medullary index*

This index represents the fineness of the cortex and allows us to evaluate bone quality.

$$\frac{\text{Epaisseur os cortical}}{\text{Diamètre extérieur du fémur}} \times 100$$

- *Femoral offset*

The femoral offset is the distance between the diaphyseal axis and the center of the femoral head.

 Glick, Y. Vancouver classification of periprosthetic hip fractures. Article reference, Radiopaedia.org. (accessed on 18 Oct 2022) <https://doi.org/10.53347/rID-52713>

**iv. METHODS AND TIMING OF EVALUATION, RECORDING AND ANALYSIS OF VARIABLES**

The table below presents the different stages and moments of patient follow-up, and the acquisition of related data.

Study Outline	Retrospective			Prospective part	
	Pre-operative data	Implantation	Immediate post-operative follow-up	Inclusion in the study	Medium-term monitoring
Topic Information				X	
Verification of inclusion criteria				X	
Demographics: Age, height, weight, sex	X				
Medical and surgical history	X				
Implantation of the prosthesis Operative report: Date of operation, type of anesthesia, approach, type of implant and assembly performed, coding of the surgical act (CCAM code)		X			
Radiological examination	X				X
Functional score assessment Modified HHS – SHO-12	X (except SHO-12)				X
Satisfaction					X
Adverse event collection		X	X	X	X

Complications and serious adverse events will be collected independently of the retrospective and prospective parts but over the entire period since the intervention.

**v. EQUIPMENT TO BE USED TO EVALUATE CI VARIABLES AND PROVISIONS FOR MAINTENANCE AND CALIBRATION MONITORING**

No specific equipment is required for the evaluation of HF variables. No additional examination is required. The radiological examination is performed prior to the follow-up visit, in local radiology centers as well as for follow-up according to standard operating procedures. In standard tracking, X-rays are taken before each follow-up.

**vi. PROCEDURES FOR REPLACING SUBJECTS, IF APPLICABLE**

N/A: This is a retrospective data collection. Subjects leaving the study will not be replaced.

**viii. END OF CI**

HF will be considered complete when the last subject has completed their single follow-up visit.  
In case of premature termination of the study, refer to Chapter 16 of this protocol.

**B. DEVICE(S) UNDER INVESTIGATION AND COMPARATOR(S)**

No comparator is used for this CI.

**i. DESCRIPTION OF EXPOSURE TO THE DEVICE(S) UNDER INVESTIGATION OR COMPARATOR(S)**

For implantation of a SAGITTA® EVL-R femoral stem in the context of hip arthroplasty, the subject may be exposed a maximum of 2 times (2 hips).

The patient is exposed, throughout the time that the implant remains in place, to the following materials:  
Titanium TA6V (ISO 5832-3) for the stem and keys.

Hydroxyapatite (ISO 13779-2 and ISO 13779-6) for stem coating.

The human tissues in contact with these materials are: femur, soft tissues, cartilage, blood vessels, and blood.

**ii. LIST OF ANY OTHER MEDICAL DEVICES OR DRUGS TO BE USED DURING HF THAT ARE NOT ALREADY LISTED IN THE INSTRUCTIONS FOR USE**

No additional drug or surgical treatment is required as part of this HF.

**iii. NUMBER OF DEVICES UNDER INVESTIGATION TO BE USED**

One (1) device is implanted per femur.

In the particular case of subjects operated bilaterally, two (2) devices may be implanted in the same subject, at a rate of one (1) per femur.

**C. TOPICS**

**i. INCLUSION CRITERIA**

- Patient of legal age on the date of surgery,
- Patient implanted with a SAGITTA® EVL-R revision femoral stem in the context of its indications between 01/01/2016 and 31/12/2018,
- Patient benefiting from a health insurance scheme.

**ii. CRITERIA FOR NON-INCLUSION**

- Patient who have not expressed consent to the collection of their data and participation in the study,
- Patient unable to understand the surgeon's instructions or perform postoperative follow-up.
- Patient with a contraindication to the use of the SAGITTA® EVL R revision femoral stem
- Patient implanted with a SAGITTA® EVL R revision femoral stem outside of their indication

**iii. CRITERIA FOR SUBJECT'S EXCLUSION**

No exclusion criteria were used in this study.

**iv. CRITERIA AND PROCEDURES FOR WITHDRAWING A SUBJECT, DISCONTINUING PARTICIPATION OR LOSING SIGHT OF A SUBJECT**

When a subject wishes to discontinue participation (for any reason), the principal investigator will be required to document the subject's exclusion or withdrawal of consent. Whenever possible, the reason for the withdrawal of consent should be recorded, especially in the case of a serious adverse event.

When a subject is excluded or if he withdraws his consent, he continues to be followed normally by his orthopaedic surgeon, as part of his normal post-operative follow-up.

All subjects for whom the principal investigator is unable to get in touch after 3 telephone reminders will be considered as 'Lost to follow-up'.

Because HF is ambispective, it is not possible to replace subjects who are lost to follow-up or excluded.

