Treatment(s)/procedure(s) related to the study	
Prospective part:
 
According to the centre's practice, as part of the systematic follow-up of hip replacement replacements, a clinical examination will be carried out with an assessment of any complications and patient satisfaction. Only a quality of life questionnaire (SHO-12) and the HHS score will be required by this HF in addition to the standard care practiced in systematic follow-up in this center. These questionnaires will be completed jointly by the patients and the surgeon (additional procedure that is neither heavy nor invasive).
 
Routine radiological evaluation will be performed. It allows the evaluation of osseointegration and bone reconstruction to document possible complications.
 
The collection of its data will be carried out in a paper case report form (CRF).
 
Retrospective part:
 
In accordance with the patient's agreement, retrospective data will be collected using the patient's medical record and will be collected in the CRF.
 
No additional examination to current practice will be carried out as part of this investigation.

Total duration of the study	The prospective portion of the study will last approximately 5 months depending on patient availability. The duration of each patient's participation in this study is limited to this single consultation. Retrospective data collection will be carried out simultaneously. This is a total duration of the study of 5 months.
Study timeline	The prospective part will begin as soon as regulatory approvals are obtained, scheduled for January 2023 and will be completed in May 2023. The retrospective part will be conducted after the patient consent has been collected. Study closure and report writing: July 2023
Statistical analysis	A statistical analysis will be carried out at the end of the study. This analysis will be carried out by SERF. A descriptive analysis will be done based on the data collected during the study. A follow-up of the events that occurred will be carried out, as well as an analysis of the survival rate according to Kaplan Meier.

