## D. PROCEDURES

### i. DESCRIPTION OF ANY HF-RELATED PROCEDURES TO WHICH SUBJECTS ARE SUBJECTED (INCLUDING DEVIATIONS FROM STANDARD CARE)

Only an additional procedure that is neither heavy nor invasive is required when participating in this HF compared to the standard care provided as part of the systematic follow-up during hip replacement revision surgery in the investigation center in question. Namely, a quality of life questionnaire (SHO-12 forgotten hip score) and a functional score (HHS Harris Hip Score) are requested in addition. These can be completed in part by the patient or collected by the investigator.

As far as the retrospective part is concerned, all the necessary data will be collected directly from the patients' medical records, the subjects having already undergone the following visits: preoperative visit, intervention, immediate postoperative follow-up. Depending on the date of the operation, one or more intermediate postoperative follow-ups may have been performed. Data on these interim follow-ups will not be collected. Only relevant data in terms of serious adverse events will be collected for these interim follow-ups.

For the prospective part, which concerns only the medium-term postoperative follow-up (minimum 4 years) taking place after the inclusion of patients in the study, the procedures to which the subjects participating in HF will be subjected are listed and briefly described below. These procedures are the same as those performed as part of the systematic follow-up of a hip replacement in the investigation center in question. At the end of the investigation, the subjects continue to be monitored according to the habits of the center.

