**iii. ANY KNOWN OR FORESEEABLE FACTORS THAT MAY AFFECT THE EFFECTS OR INTERPRETATION OF THE RESULTS**

The observational nature of HF and its duration can have several consequences on its outcomes. First, a high number of patients who have been lost to follow-up or died are expected.

However, replacement of patients who have been lost to follow-up or who have died is not considered due to the ambispective nature of the study.

The bias inherent in the retrospective part could also limit the quality of the data collected.

As the study is observational, factors such as age, associated comorbidities or any other confounding factors, will be taken into account during the analysis of the data.

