## iii. CALCULATION OF THE SURVIVAL RATE

The Kaplan-Meier analysis is based on the calculation of cumulative conditional probabilities. The survival rate will be calculated using the following formula:

$$S_{t(i)} = \prod_{t(i-1) < t(i)} S_{\frac{t(i)}{t(i-1)}} = \prod_{t(i-1) < t(i)} 1 - \frac{D_i}{N_i}$$

With:

- $S_{t(i)}$ , the probability of having the implant in place so far;  $t_{(i)}$
- $S_{\frac{t(i)}{t(i-1)}}$ , the probability of still having the implant in place knowing that the implant was in place at  $t_{(i-1)}$  to  $t_{(i)}$
- $D_i = 1 - N_{s(i)}$ , the number of subjects who required removal or change of implant, observed at the time;  $t_{(i)}$
- $N_{s(i)}$ , the number of subjects with their implant still in place at the time observed at the time;  $t_{(i)}$
- $N_i = N_{s(i-1)} - D_i - C_i$ , the number of subjects at risk of implant removal or change, observed at time;  $t_{(i)}$
- $C_i$ , the number of censored subjects (lost to follow-up, deceased, having left the study) observed between time and  $t_{(i-1)}$  to  $t_{(i)}$

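### No date of last event-free contact is planned for lost patients, so if they enter the Kaplan-Meier analysis the stem survival estimate can be biased in either direction

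*Protocol*

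**What the plan says.** - **Who is censored.** Section 7.C.iii (survival rate) defines C as "the number of censored subjects (lost to follow-up, deceased, having left the study) observed between time" points. It attaches no calendar or clinical date to the loss.
- **What loss means.** Section 6.C.iv gives the only definition: subjects the investigator is "unable to get in touch after 3 telephone reminders will be considered as 'Lost to follow-up".
- **When that happens.** The synopsis has the prospective part "scheduled for January 2023 and will be completed in May 2023". Eligible stems were implanted "in the context of its indications between 01/01/2016 and 31/12/2018" (section 6.C.i).
- **What is kept from the years between.** Section 6.D.i says "Data on these interim follow-ups will not be collected", then makes one exception: "Only relevant data in terms of serious adverse events will be collected for these interim follow-ups". The schedule in section 6.A.iv has no column between the immediate postoperative follow-up and the medium-term visit. Its footnote, like the Complications paragraph of section 6.A.iii, collects complications and serious adverse events over the whole period since surgery.
- **How much loss is foreseen.** Section 6.D.iii warns that "a high number of patients who have been lost to follow-up or died are expected", without a figure.
- **Who enters the data.** Sections 6.C.ii, 6.C.v and 6.C.viii restrict inclusion and data collection to patients who are offered participation at the follow-up visit and consent.

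**The concern.** A lost patient should leave the risk set on the last date when the stem was known to be in place. For a patient who cannot be reached in 2023, that date may lie years before the recall. The collection rule is asymmetric: an interim revision known to the centre is recorded as a serious adverse event, while an interim visit at which nothing was wrong leaves no trace in the study data.

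An analyst following this plan would have two dates for an event-free lost patient. The recall counts unobserved years as years of stem survival. The immediate postoperative visit discards real event-free time but keeps the failures that occurred during it. The two errors go in opposite directions, and both fall on the primary outcome. A later statistical analysis plan can choose a censoring rule, but it cannot use a date that the protocol says is not collected.

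**Working it through.** **Time span.** The shortest interval is 31/12/2018 to 01/01/2023, 4.0 years. The longest is 01/01/2016 to 31/05/2023, 7.4 years.

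**Inputs from the protocol.** Reference revision rate 15.2% at 5 years and 20.8% at 10 years (section 3.A); about 120 implants (section 7.E). The protocol has no calculated figure on this point to reproduce.

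**Assumptions (not in the protocol).** Fraction lost L = 10–40%. Last contact s uniform over 0–2 or 0–4 years. Loss unrelated to revision. Implantation uniform over 2016–2018. Immediate postoperative visit at about 0.1 year. Two shapes for the true revision curve F, both giving F(5) = 15.2%:
- constant hazard, h = −ln(0.848)/5 = 0.0330 per year;
- early failure, a Weibull through both section 3.A figures: shape = ln[ln(0.792)/ln(0.848)]/ln 2 = 0.50, so F(t) = 1 − exp(−0.0737·√t).

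**Censoring at the recall, no later revision seen.** The lost contribute events only up to s, so the estimate at 5 years tends to (1 − L)·F(5) + L·E[F(s)]. For L = 20%, the first term is 0.8 × 15.2% = 12.16%.

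| Curve | Last contact | E[F(s)] | Estimate at 5 years |
|---|---|---|---|
| Constant hazard | 0–2 years | 3.2% | 12.16 + 0.2 × 3.2 = 12.8% |
| Constant hazard | 0–4 years | 6.3% | 12.16 + 0.2 × 6.3 = 13.4% |
| Early failure | 0–2 years | 6.7% | 12.16 + 0.2 × 6.7 = 13.5% |
| Early failure | 0–4 years | 9.3% | 12.16 + 0.2 × 9.3 = 14.0% |

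If half of the later revisions are captured, the bias halves: (12.8 + 15.2)/2 = 14.0% up to (14.0 + 15.2)/2 = 14.6%. If all are captured, it is zero.

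**Censoring at the immediate postoperative visit.** After that visit, lost patients stay in the risk set only if they will have a recorded revision before s. With S = 1 − F and f the density, the hazard being estimated at time u is f(u)·[(1 − L) + L·P(s > u)] / [(1 − L)·S(u) + L·P(u < T ≤ s)]. From 4 years on, administrative censoring also multiplies the (1 − L) terms. This exceeds the true hazard f(u)/S(u) while u is below the longest last-contact time. Numerical integration gives the second column below.

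| Lost | Censored at recall, none captured | Censored at immediate postoperative visit | Censored at last contact |
|---|---|---|---|
| 10% | 14.0–14.6% | 15.5–15.9% | 15.2% |
| 20% | 12.8–14.0% | 15.8–16.7% | 15.2% |
| 30% | 11.6–13.4% | 16.2–17.7% | 15.2% |
| 40% | 10.4–12.8% | 16.8–19.1% | 15.2% |

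**Lost patients never included.** The estimate is 15.2% if loss is unrelated to revision. Otherwise the bias comes from selection, and its direction is unknown.

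**Scale.** The interval formula in section 7.C.i, at p = 15.2% and n = 120, gives 0.152 ± 1.96 × √(0.152 × 0.848/120) = 8.8% to 21.6%.

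**The case against.** The strongest objection is that the protocol never orders censoring in 2023. Section 6.C.iv defines a status, section 7.C.iii counts the censored in each interval, and neither fixes a date; a censoring convention commonly goes into the statistical analysis plan, which is not shown. This stands. A reader might infer from the reminder rule that lost patients are credited with unobserved years and that revision is therefore understated. The documents do not support that as a statement of fact. What remains is not the missing convention but the stated decision to leave out the interim data on which any sound convention would rest.

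Second, revisions are not invisible. Sections 6.A.iii, 6.A.iv and 6.D.i collect complications and serious adverse events since surgery, and a revision operation meets the hospitalization criterion in section 14.A. This also stands: revisions in the centre's records should be captured, and the unseen ones are mainly those done elsewhere after contact ended. The no-capture figures are therefore an upper bound on the recall-censoring bias.

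Third, unreachable patients may never enter. Participation is offered at the visit and data are collected only from those who agree, so someone who cannot be telephoned would contribute no person-time. That is a fair reading of sections 6.C.ii, 6.C.v and 6.C.viii. It conflicts with section 7.C.iii, which lists the lost and deceased among the censored, and with section 6.C.iv, which calls unreachable people subjects. The protocol does not settle the matter.

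Finally, the shift is small beside the sampling interval, and no test or success criterion depends on 15.2% (sections 7.D and 7.G). True, but the bias is systematic, grows with loss and is cheap to prevent.

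**Conclusion.** The point holds conditionally. For any lost subject who is analysed, the planned data support two censoring times, and each can bias the primary estimate. At an assumed 20% loss with no later revision captured, recall censoring turns a true 15.2% at 5 years into about 12.8–14.0%, which is 1.2–2.4 points or 8–16% too low. Immediate-postoperative censoring gives about 15.8–16.7%, which is 0.6–1.5 points too high. Last-contact censoring gives about 15.2%.

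The loss fraction, last-contact times and degree of capture are assumptions, and loss is taken as unrelated to revision. The recall-censoring bias falls to zero if every later revision is captured, and neither bias arises if unreachable patients are never included. The supportable conclusion is that survival may be misstated, with a direction that depends on the date chosen. The protocol should be changed, but the point does not invalidate the study.

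**What to change.** 1. In sections 6.A.iv and 6.D.i, add one item for every patient in the analysis: the last date on which the stem was documented in place, from a visit or a radiograph.
2. In section 7.C.iii, censor lost and withdrawn subjects at that date. Censor deceased subjects at death only if stem status up to death is known, and otherwise at that same date.
3. Report the number lost and their median time to last contact beside the survival curve.
4. Reconcile sections 6.C.ii, 6.C.v and 6.C.viii with sections 6.D.iii and 7.C.iii on whether unreachable and deceased patients are in the analysis.

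The cost is one date per patient from the medical record that the retrospective part already uses, plus a few sentences. The confidence interval widens slightly: in simulated cohorts of 120 with 20% lost, the standard deviation of the 5-year estimate rose from 3.1 points with recall censoring to about 3.5 with last-contact censoring. The survival figure may also be less favourable than under recall censoring.
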